### Study Procedures – Intervention Arm and Control Arm Sequential description

As described in the recruitment section of this application, potential research participants are identified via the KPWHRI VDW by the KPWA programmer and sent a letter of invitation, a study information sheet, study insert, and a \$2 incentive. Five days after the invite letter is sent, the KPWA survey team calls subjects for the first screening. Participants will be screened twice. First, they will be screened on basic eligibility criteria when the survey research program calls them to recruit. (See STRIPE screening

script for screening questions.) If the participant passes the first round of screening and is still interested, they will be scheduled for a second round of screening with a study research specialist.

Prior to the call, the study team will mail the participant a copy of the consent form and a cover letter. During the second screening call, the research specialist will ask sensitive eligibility questions regarding recent intent to harm and recent psychiatric hospitalization. (see "Pre-randomization script" for sensitive eligibility screening script and questions). If the participant passes this round of screening, the research specialist will administer and obtain oral consent. The participant will then be offered the baseline survey via phone or web. If phone is chosen, the participant will be asked if they would like to do the baseline survey now or schedule a time to complete it. If web is chosen, the research specialist will confirm the participants email address and email them a link to the survey. Reminder emails and/or phone follow-up will occur if subjects do not complete the baseline survey.

Once the baseline survey is complete, we will randomize the participant into the intervention arm or the control arm. The study team wants participants to be randomized after the baseline survey out of concern that knowledge of status could affect a subject's responses to questions and participation in the baseline assessment. We will send participants a thank you letter with their incentive upon completion of the baseline assessment that details which arm they were assigned to and next steps.

We anticipate the time from the letter being mailed to time of enrollment to be between 2-4 weeks. All invitation materials, consent forms, HIPAA authorization forms and scripts are attached in this package.

After the baseline assessment and randomization, all participants will be asked to take two more surveys; 6 months after enrollment and 12 months after enrollment. The survey can be taken either in web form or on the telephone, administered by a survey research program telephone interviewer. With the 12 month phone or web survey reminder letter, all participants will receive a \$2 pre-incentive. The survey will ask questions about physical health (including any experience with pain), mental health (depression and anxiety), and medication use. All baseline, 6-month, and 12-month surveys including script are included in this packet. See Master Survey document for a list of the surveys to be administered at the three-time points.

Additionally, all subjects enrolled in the intervention who choose to taper their opioids arm will be asked to complete the two item Graded Chronic Pain Scale (GCPS) and the fourteen item Hospital Anxiety and Depression Scale (HADS) before each intervention telephone session. (See Measures for Intervention Arm only doc.). Surveys are attached in this package. The pre-visit GCPS and HADS will be completed on paper (mailed with intervention packet materials) prior to the visit and read their score to the research interventionist at the beginning of the session.

Activity	Time Commitment
----------	-----------------

Read invitation packet	5 minutes
1 st screening call	10 minutes
Read consent packet and answer any questions	10 minutes
2 nd screening call including consent and randomization	20 minutes
Baseline survey	30 minutes
Pre-visit GCPS and HADS for participants who choose to taper	5 minutes each visit 5-18
Intervention arm study visit 1-18	30-60 minutes each visit
6 month survey	20 minutes
12 month survey	20 minutes

We anticipate it will take 18 months to enroll all 250 study participants. Each participant will be followed for 12-months post randomization.

#### Device/drug information

N/A

#### Secondary data: data, sources, and date range

In addition to the primary data described above, secondary data to be collected on participants enrolled in both arms of the study are listed in the table below.

#### Data from KP Washington

Source (specify) (i.e., from KPWA, or from an existing or previous study)	Key Information/Description of Variables	Date Range
KPWA data sources (VDW)	Diagnoses via ICD codes and dates of code: Comorbidities (comorbidity indices and the individual constituent diseases), mental health disorders (e.g. depression, anxiety), substance use disorders (e.g. opioid use disorder, alcohol use disorder, tobacco use disorder, cannabis use disorder, stimulant use disorder),	2016-2022

	cancer, suicidal ideation, and pain including site of pain	
KPWA data sources (VDW)	Social history table variables for alcohol use and tobacco use	2016-2022
KPWA data sources (VDW)	Health plan enrollment information (start and stop dates)	2016-2022
KPWA data sources (VDW)	Health care utilization including: outpatient, inpatient, emergency department	2016-2022
KPWA data sources (VDW)	Medication orders and pharmacy dispensings including dates	2016-2022
KPWA data sources (VDW)	Laboratory tests and results	2016-2022

DIRECT IDENTIFIERS			
 Names  Dates  Postal address  Geocode  Phone numbers  Fax numbers  Email address	 Social Security Numbers  Medical record numbers  Health plan numbers  Account numbers  License/Certificate numbers  Vehicle ID numbers  Device identifiers/Serial numbers	 Web URLs  IP address numbers  Biometric identifiers (e.g., finger prints, voice prints, retina scans)  Facial Photos/Images  CHS ID  Other unique identifier(s):	

**Alternative treatment(s) and/or denied treatment**

N/A

**Deception/incomplete disclosure**

N/A

**Incidental findings**

N/A

**Procedures to monitor, lessen or mitigate risk**

There are several study design features that lessen or mitigate risk:

- Participants assigned to the control group may be disappointed with their assignment. We are providing incentives for completing 6 and 12 months surveys for both groups to improve retention in the trial.
- Participants may be embarrassed or psychologically distressed at the survey questions, they are told that they can skip any questions they do not want to answer
- Breach of confidentiality is a potential risk. See section 5u for a description of the various controls set in place to safeguard data security. Additionally, staff are trained on best practice privacy and confidentiality measures.
- The study will have a plan in place to handle Critical Incidents, when a participant endorses intent to harm themselves or others. Although, we anticipate this to be rare, we would like to be prepared in the event that a participant spontaneously endorses intent to harm. The research specialist and research interventionist will administer the Columbia Suicidality Severity Rating Scale. After determining the score, the research interventionist will take the appropriate steps to triage the participant per the study protocol. (see CI procedures for Columbia Suicidality Severity Rating Scale and general CI procedures). Additionally, the research specialist and research interventionist will be supervised by a KPW licensed clinical psychologist. [name] is KPWA mental health provider. All critical incidents will be reviewed by the study psychologist.
- A data use agreement will be in place to share study data with investigators at the University of Washington

### **Subject drop out or withdrawal procedures**

If a subject drops out or we withdraw them from the study, the study team will:

- Update the tracking database to indicate that no further patient-self report data collection or participant contact will occur. They will not be asked to complete any more surveys. If we withdraw the participant from the study, we will send them a letter notifying them that they are no longer enrolled in the study.
- We will continue to use the data they have already contributed/agreed to allow us to use per their consent for analyses
- All participants using buprenorphine for treatment of OUD will be withdrawn from the entire study. We may learn about buprenorphine use from the screening survey or as indicated in VDW medication dispensing data ascertained prior to the analyses. Primary data collection will cease and they will not be included in analyses. This is an exclusion criteria.
- All pregnant women will be withdrawn from the study entirely. Primary data collection will cease and they will not be included in analyses. Pregnancy status will be determined via a screening question and diagnosis codes from the VDW for subjects in both study arm prior to analyses. We expect very few young women to be in the study due to the average age of chronic high dose opioid users at KP.

### **Anticipated study end date**

The anticipated study end date for the completion of primary analyses will be on or before December 31, 2021

## **Study Procedures – Intervention Arm**

### **Sequential description**

After subjects are randomized into the intervention arm, they will receive a letter with their randomization status, intervention packet, and then begin having telephone visits with the study research interventionist. The study team will send a letter to the participants PCP noting their participation in the pain self-management training arm of the trial. Prior to their first telephone call we will send participants a packet containing, "The Pain Survival Guide" <https://www.amazon.com/Pain-Survival-Guide-Reclaim-LifeTools-ebook/dp/B0029KHTK8>, a CD containing audio files of relaxation techniques and participant workbook that includes the various exercises for each visit along with GCPS and HADS questionnaires to administer before each telephone visit. Participants can opt to receive and take the GCPS and HADS questionnaires on the web if they choose. The workbook, CD and questionnaires are included in this package. Additionally, we are working on creating a study website that will host the audio files.

A description of each telephone visit, the timing of the visit and the duration of the visit is described in the following table. See the "Clinician Manual" for details on the content for each session.

Session number	Week (from randomization)	Session content	Duration
1	1	Overview of intervention and sessions, education regarding benefits of pain coping skills training and collaborative nature of treatment. Identification of treatment goals. Instruction and practice in diaphragmatic breathing. Personal action plan introduction. Review of study team contacts Review pre-visit GCPS and HADS assessments to be done prior to each subsequent session	60 mi
2	2	Diaphragmatic breathing review and practice. Education regarding rationale for and benefits of relaxation techniques, introduction to 7-muscle group tense-release progressive muscle relaxation.	30 min
3	3	Pain neuroscience education and rationale for cognitive and behavioral techniques for managing pain. Education about and discussion of harm and fear-avoidance beliefs. Home assignment: watch two videos and read article about patient opioid taper experiences.	30 min
4	4	Motivational interviewing: elicit history of opioid use and views about tapering, provide education about long-term opioid therapy risks and scientific evidence for benefits, discuss and problem-solve barriers to tapering. Education about withdrawal symptoms. --debriefing of subject after viewing videos at home of patient experiences tapering off opioids. --If interested in taper, subject instructed to make appointment with primary care provider at the time of their next opioid refill to discuss taper and subject informed interventionist will communicate with PCP about this, as well as with the study PI, a psychiatrist with expertise in pain, who will review their medications and may make suggestions about their medications. To be asked at subsequent sessions if patient is not interested in tapering starting at session 4. -- If pt interested in taper, interventionist provides to Study PI information on EHR diagnoses, pain rating (graded chronic pain scale - GCPS), anxiety and depression score	45 min

		(HADS). After consultation with Study PI [name], interventionist provides guidance to primary care provider about taper discussion, opioid taper plan, and initiation or adjustment of non-opioid medications to relieve pain, anxiety, depression, insomnia. See Taper Guidelines for details. --If not interested, interventionist will ask about interest at subsequent sessions as deemed appropriate.	
5	5	Education about relationship between sleep and pain, sleep hygiene, and cognitive and behavioral strategies for improving sleep.	30 min
6	6	Review of cognitive and behavioral skills taught to date, and application to daily life to manage pain and stress. Concept that hurt ≠ harm.	30 min
7	8	Education about benefits of activity pacing. Development of individual activity pacing plan for the participant.	30 min
8	10	Coping with pain flare-ups: development of personal pain coping plan.	30 min
9	12	Instruction and practice in 4-muscle group tense-release progressive muscle relaxation	30 min
10	14	Instruction in and practice of 4-muscle group progressive muscle relaxation without tensing.	30 min
11	18	Education about coping self-statements and identification of helpful coping self-statements for the individual participant.	30 min
12	22	Distraction as a pain coping skill.	30 min
13	26	Instruction and practice in body scan technique.	30 min
14	30	Instruction and practice in mini-relaxations.	30 min
15	34	Review and practice of mini-relaxation, and application to daily situations of increased pain or stress.	30 min
16	38	Education about importance of pleasurable activities, identification of pleasurable and meaningful activities for the individual participant, education about goal setting, pleasurable activity goal-setting. Review of daily plan and pain coping flare-ups plan; refinement and revision as necessary. Pain coping skills review.	30 min
17	42	Review of pain coping skills learned in this program. Education about maintenance of gains and relapse prevention.	30 min
18	46	Skills summary, final plan for maintaining gains and managing setbacks and pain flare-ups. Discussion of participant's thoughts about this being the last session, and reminders of next steps in the research.	30 min

Note: The first 6 sessions are weekly. The next 4 sessions are biweekly. The remaining sessions are monthly. For participants who are tapering their opioid dose, each session will include discussion of how that is going and how the pain coping skills might be used to manage pain and any other symptoms experienced. Each session includes home activity assignments for reading (The Pain Survival Guide and participant workbook) and coping skills practice (personal action plan) and review of experiences with the previous week's assignments. Each session also includes identification of obstacles or challenges to completing the home activity assignments and problem-solving ways to overcome these. Intervention participants will be provided a workbook, The Pain Survival Guide, access to audio files of relaxation exercises, and access to two videos of patient interviews.

#### Primary Data Collected on the Intervention

During each telephone session, the research interventionist will track the phone sessions into the project REDCap tracking data base hosted at KPWA. The information captured at the visits includes:

- Date of the phone visit

- Whether or not the participant attended their scheduled appointment
- Check boxes for session content that was covered during the visit
- Any critical incidents (intent to harm oneself or other)
- Any adverse events
- Detailed notes on the visit
- Amount of time spent on each visit
- HADS and GCPS score ( score read to interventionist and entered into REDCap at the beginning of each session for participants who choose to taper)

At the fourth study visit, the research interventionist will ask participants if they want to taper their opioid dosing. If the participant declines to taper, they will proceed with the rest of their pain self-management sessions and follow-up surveys. If a participant expresses interest in tapering, the interventionist will recommend medication taper suggestion to the participant's PCP using Epic Telephone Encounters. We will provide taper support at a later date if they prefer to delay the taper or resume paused tapers. Patients will be allowed to pause tapers (i.e., put the taper on hold) for any reason including the need to escalate opioid dose (e.g., surgery requiring additional pain management). Patients delaying or pausing tapers will still continue to receive the pain self-management training. Participants will be informed of the risk of stock-piling opiates during the taper process. The research interventionist may need to consult with [name], the study research physician on complicated tapering scenarios. [name] will have Epic read only access to review the medical records of any difficult tapering sessions to provide guidance to the research interventionist. The guideline for tapering was developed by [name] (UW psychiatrist and Principal Investigator), and is attached. The guidelines were reviewed by [name] (KP Medical Director, Continuum of Care), [name] (Family Medicine Physician and Medical Director, Clinical Knowledge Development and Support), [name] (Family Medicine provider, Program Chief of Family Medicine, study Co-Investigator) and [name], BCACP (Pharmacy Clinical Coordinator, Quality and Clinical Operations). This taper guideline is consistent with KPWA guidelines for COT tapering.

Prior to opioid tapering, the research interventionist will follow the Communication Plan for points to cover with both the patient and provider.

A random sample of the intervention visits will be chosen for quality assurance activities. We will send audio files of the visit to [name] at the University of Washington using the KPW secure file transfer site. The purpose of the QA is to ensure the research interventionist is conducting the telephone visits correctly according to protocol. During the telephone visit, the research interventionist will inform the participant that they will not use the participant's full name in session and the recordings will be labeled with a study id and date; not their name.

#### Primary Data Collected on Opioid Tapering for a Subgroup of Patients Electing to Taper

During the opioid taper, [name] will be responsible for managing the tapering plan.

The research interventionist will meet with [name] weekly and together they will track specifics about the taper into the project REDCap tracking data base hosted at KPWA. This data will come from the patient and provider interactions and the electronic medical record. The information captured in REDCap at the visits that are specific to tapering includes:

- Details on the taper each week

- Taper start date
- Current opioid medication(s) name and dose per day in morphine equivalents
- Taper recommendations: opioid taper plan, specific opioid taper recommendations (see Taper Guidelines)
- Other medication recommendations: drug name and dose (see Taper Guidelines and KPWA guidelines)
- Provider implemented recommendations for taper: yes, no, no response
- Provider implemented recommendations for supportive medications for the taper: yes, no, no response
- Taper paused (i.e., put on hold) (yes, no)
  - Reason for pause (dose escalation, patient preference, provider preference, pain, other symptoms, etc.)
- Taper resumed (yes, no, date)

**Device/drug information**

N/A

**Secondary data: data, sources, and date range**

Additional secondary data other than what is described in the “Study Procedures – Intervention Arm and Control Arm” will be collected and entered into REDCap on participants enrolled in the intervention arm as outlined in the table below.

**Data from KP Washington**

Source (specify) (i.e., from KPWA, or from an existing or previous study)	Key Information/Description of Variables	Date Range
KPWA data sources (Epic)	Current problem list	2018-2021
KPWA data sources (Epic)	Current medication list	2018-2021

**DIRECT IDENTIFIERS**

 Names	 Social Security Numbers	 Web URLs
 Dates	 Medical record numbers	 IP address numbers
 Postal address	 Health plan numbers	 Biometric identifiers (e.g., finger prints, voice prints, retina scans)
 Geocode	 Account numbers	 Facial Photos/Images
 Phone numbers	 License/Certificate numbers	 CHS ID
 Fax numbers	 Vehicle ID numbers	 Other unique identifier(s):
 Email address	 Device identifiers/Serial numbers	

**Alternative treatment(s) and/or denied treatment**

N/A

**Deception/incomplete disclosure**

N/A

**Incidental findings**

N/A

**Procedures to monitor, lessen or mitigate risk**

There are several study design features that lessen or mitigate risk:

- Participants may be embarrassed or psychologically distressed at some of the survey questions, they are told that they can skip any questions they do not want to answer
- Breach of confidentiality is a potential risk. See section 5u for a description of the various controls set in place to safeguard data security. Additionally, staff are trained on best practice privacy and confidentiality measures.
- Participants may feel increased pain while they are tapering. If the participant experiences increased pain due to the condition for which they are on COT, the research interventionist may consult with [name] and the participant's PCP to evaluate and provide assistance.
- While very unlikely with the planned gradual taper, participants may experience opioid withdrawal and can call the research interventionist to discuss these symptoms. The research interventionist will consult with [name] (PI) and work closely with the participant's PCP to recommend medications to provide comfort from withdrawal symptoms.
- The study will have a plan in place to handle Critical Incidents, when a participant endorses intent to harm themselves. The research interventionist (PA) will administer the Columbia Suicidality Severity Rating Scale. After determining the score, the research interventionist will take the appropriate steps to triage the participant per the study protocol and KPWA guidelines. Additionally, the research interventionist will be supervised by a KPWA licensed clinical psychologist. All critical incidents will be reviewed by the study psychologist. The protocol for handling critical incidents is including in this package.
- A data use agreement will be in place to share study data with investigators at the University of Washington

## Subject drop out or withdrawal procedures

If a subject drops out or we withdraw them from the study, the study team will:

- Update the tracking database to indicate that no further patient-self report data collection or participant contact will occur.
- We will continue to use the data they have already contributed/agreed to allow us to use per their consent for analyses
- We will not ask them to complete any additional surveys or attend study visits (if applicable)

In rare instances, the study PI's may decide to withdraw a participant from the study and analyses. The reasons for removing participants from the study and analyses would be:

- Concern about data validity. Examples of the types of scenarios are when a participant's behavior indicates that they may not be answering questions truthfully either due to deceit, they are high on drugs during their scheduled visit or there is a medical condition like narcolepsy that makes it difficult for them stay awake during their scheduled appointment.
  - The research interventionist would bring concerns about data validity to the study team and the PI would make the determination on whether to withdraw or not. The study team will send them a letter informing them of their withdrawal.
- All participants using buprenorphine for treatment of OUD will be withdrawn from the entire study. Primary data collection will cease and they will not be included in analyses. While buprenorphine is a partial opioid, it is indicated for the treatment of opioid use disorder and rarely if ever used to treat pain at KPWA. Patients treated with buprenorphine for OUD are complicated and are either no longer on other opioids or being tapered off other opioids by the provider treating their OUD. They are not part of our study population of interest and thus buprenorphine use is both an exclusion criteria and reason for being withdrawn from the study.
  - If the research interventionist learns that the participant is taking buprenorphine for OUD, they would bring that information to the study team and the PI would withdraw the participant from the study. The study team will send them a letter informing them of their withdrawal.
  - Similarly, patients in both the intervention and control arm will be removed from the entire study and analyses if they are using buprenorphine as indicated in VDW medication dispensing data ascertained prior to the analyses.
- All pregnant women will be withdrawn from the study entirely. Primary data collection will cease and they will not be included in analyses. Pregnancy status will be determined via diagnosis codes from the VDW for subjects in both study arm prior to analyses. The research interventionist may also learn of pregnancy through the EMR, PCP, or self-report from the participant. We expect very few young women to be in the study due to the average age of chronic high dose opioid users at KP.

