### **Study Procedures –Control Arm**

#### **Sequential description**

Participants randomized to the control arm (i.e. usual care only) will not receive any intervention visits. They will only complete the three surveys described above in the “Study Procedures – Intervention Arm and Control Arm” section.

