##### **a. Data Analysis**

Describe the data analysis plan, including:

- Statistical procedures.
- When applicable, the power analysis.
- Any procedures that will be used for quality control of collected data.

We will use descriptive statistics to characterize the sample at baseline. To address the trial's effectiveness aims, we will use an intent-to-treat approach (i.e., individuals will be analyzed according to randomized group regardless of participation in any opioid taper support sessions). We will also use a complete case analysis (i.e., that includes those participants who have observed follow-up outcome data) since we expect at least 85% follow-up at 12 months (primary time-point).

To compare each of the primary outcome measures (opioid dose and PEG score) between intervention groups the following linear regression model will be constructed:  $E(Y_{ij}) = \beta_0 + \beta_1 Trt_i + \beta_2 Time_j + \beta_3 Trt_i \times Time_j + \alpha_z Z_i$ , where  $Y_{ij}$  is the outcome for person  $i$  at time  $j$  ( $j=6$  or 12 months),  $Trt_i$  is the dichotomous intervention effect of interest (with control arm as the referent group),  $Time_j$  is the dichotomous variable indicating the 6- or 12-month time point,  $Trt_i \times Time_j$  is the interaction between the treatment and time point indicators and  $Z_i$  is a vector of baseline covariates that we a priori plan to adjust for including age, gender, baseline opioid dose group, whether they were referred to COMET, and KPWA clinic. We will include both 6- and 12-month time-points in a single model to improve statistical efficiency, but the 12-month time point is considered primary. We will fit the linear regression model using GEE with robust standard errors to account for the multiple time points in a single model. We will use two-sided tests at the 0.05 level. Arguments against adjusting for multiple comparisons for two co-primary outcomes have been made by Rothman and others. (Rothman KJ. No adjustments are needed for multiple comparisons. *Epidemiology*. 1990;1:43–46) For each outcome, we will report the adjusted mean difference between treatment groups and its 95% confidence interval.

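### Data-validity removals from the analyses are discretionary and, in practice, fall on the intervention arm, an unreconciled departure from intent-to-treat

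*Combined protocol and SAP*

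**What the plan says.** The withdrawal procedures under Study Procedures – Intervention Arm present these removals as exceptional ("In rare instances, the study PI's may decide to withdraw a participant") but extend them to the analyses: "the study PI's may decide to withdraw a participant from the study and analyses". The reason is "Concern about data validity", defined only by examples: untruthful answers, a participant of whom it is said that "they are high on drugs during their scheduled visit", and a condition such as narcolepsy that prevents staying awake at an appointment. The route is that "The research interventionist would bring concerns about data validity to the study team", after which "the PI would make the determination on whether to withdraw or not". No criterion, time limit, cap, blinding or independent adjudication is stated.

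Under Study Procedures – Control Arm, control participants "will not receive any intervention visits". The withdrawal text there covers only an update of the tracking database. The withdrawal text for both arms together contains removals for buprenorphine and for pregnancy, both checked in both arms through the Virtual Data Warehouse (VDW), but no data-validity removal.

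Section 6.a, Data Analysis, promises intent-to-treat, explained as meaning that "individuals will be analyzed according to randomized group regardless of participation in any opioid taper support sessions".

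**The concern.** The stated trigger is behaviour at a scheduled session, seen by someone who deals only with the intervention arm. A control participant who behaves in the same way has no session at which to be noticed and no written route to removal. The decision is made knowing the arm, since the report comes from a session. It can also be made knowing how the taper is going: the session table has the study PI consulted on tapers and runs to week 46.

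Two of the examples, intoxication and deceit, lie close to problem opioid use, which is a hypothesised outcome in section 2 and is related to the substance-use-disorder subgroup in section 6.a. Removing such people from one arm would make that arm look better with no true effect.

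The rationale also fits the remedy poorly. The 6- and 12-month surveys are taken on the web or with a survey-program interviewer, not with the interventionist. Medication orders and dispensings come from the VDW in both arms. Alertness or candour on a training call says little about those data, yet removal discards them all. None of the sensitivity analyses in section 6.a would bring the removed participants back.

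**Working it through.** **Inputs from the documents.** 125 per arm (section 5.a); 86 evaluable per arm, dose SD 34 mg, target difference 20 mg, PEG difference 1.2 with SD 2.5 (Sample Size); two-sided 0.05 level (section 6.a).

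**Assumptions, because the plan gives no figure.** The number removed, k; problem use of 20% in both arms; no true effect; and how the removed differ from the retained.

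**The plan's own figures.** There is none for removals. The power statements reproduce adequately with power = Φ(Δ/(σ√(2/n)) − 1.96) and n = 86:
- Dose: 20/(34 × 0.1525) = 3.86, giving 97.1% (stated: above 90%).
- PEG: 1.2/(2.5 × 0.1525) = 3.15, giving 88.3% (stated: approximately 90%).

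**Problem opioid use.** With 25 problem users among 125 in each arm, the retained proportion is (25 − k)/(125 − k) if every removed person is a problem user, and (25 − k/2)/(125 − k) if half are. Dividing by 20% gives the spurious relative risk (RR).

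| k removed | Retained proportion, all problem users | RR | RR if half are problem users |
|---|---|---|---|
| 2 | 23/123 = 18.7% | 0.93 | 0.98 |
| 4 | 21/121 = 17.4% | 0.87 | 0.95 |
| 6 | 19/119 = 16.0% | 0.80 | 0.92 |

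The result depends on the assumed prevalence p. With a fraction f removed, all problem users, RR = (p − f)/((1 − f)p). For p = 10%, 20% and 30% this is 0.82, 0.92 and 0.95 at f = 2%, and 0.53, 0.79 and 0.88 at f = 5%.

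**Dose.** If those removed average 34 mg (one SD) above the arm mean, the retained mean falls by k/(125 − k) × 34 mg:
- k = 2: 0.6 mg
- k = 4: 1.1 mg
- k = 6: 1.7 mg

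The last two are 6% and 9% of the 20 mg target. These are unadjusted. The model adjusts for baseline opioid dose group, so any excess already present at baseline would be partly absorbed.

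**Type I error.** Take the shift over its standard error, σ√(1/n + 1/(n − k)), in a normal approximation. With 125 per arm and the dose shifts above, the error is about 5.2%, 5.8% and 6.8%. With 86 per arm, let the removed differ from the retained by 0.5 to 1 SD:

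| k of 86 | Dose bias (mg) | PEG bias (points) | Type I error |
|---|---|---|---|
| 2 | 0.4 to 0.8 | 0.03 to 0.06 | 5.1% to 5.3% |
| 4 | 0.8 to 1.6 | 0.06 to 0.12 | 5.3% to about 6.0% |
| 9 | 1.8 to 3.6 | 0.13 to 0.26 | 6.3% to 10.2% |

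The last row, about 10% removed, is hard to square with removals described as rare.

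**What deleting the analysis exclusion alone would achieve.** The same withdrawal section stops all further surveys once a participant is withdrawn, and the primary analysis in section 6.a is complete-case. Such a participant would then have no later PEG score and would still drop out of that co-primary analysis. The remedy therefore has to cover follow-up as well.

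**The case against.** The strongest reply is that this is a rarely used safeguard with little effect on the trial's main results. That largely stands for the co-primary outcomes: at 2% to 5% removed, type I error stays between about 5% and 6%. Problem opioid use, where the effect could be larger, is not a primary outcome.

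Four stronger readings are tempting and are not supported.
- A reader might infer that the plan exempts controls. No sentence says so. The rule speaks of a participant, its examples are not exhaustive, and controls who choose telephone surveys do speak to interviewers. What the text supports is narrower: the only stated route runs through the interventionist, and no parallel route is written for controls.
- A reader might take a relative risk of 0.80 as the expected bias. It needs six removals, all of them problem users (6 of 25, or 24%), and an assumed prevalence. Narcolepsy and untruthful answers are not in themselves problem opioid use.
- A reader might infer that dose and PEG are certainly biased towards the intervention. Nothing in the documents says that people who seem intoxicated, drowsy or deceitful have higher doses or worse PEG scores.
- A reader might see a flat contradiction with the statement in the same section that data already contributed will still be used. That is the general rule, and the data-validity paragraph can be read as an exception to it.

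What remains is that the exception has no criterion or cap, is decided with the arm known, and is nowhere reconciled with the intent-to-treat statement.

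**Conclusion.** The point holds and should be fixed. As written, the plan allows a post-randomisation exclusion from the analyses, at the PI's discretion and with the arm known, that in practice falls on the intervention arm. That one-arm reach is a strong inference from the stated trigger and reporting route. The exclusion departs from analysis as randomised.

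Problem opioid use is the outcome most exposed, plausibly in the intervention's favour: a relative risk of 0.93 to 0.80 for 2 to 6 removals in the worst case with 20% prevalence, and 0.98 to 0.92 if half of those removed are problem users. For dose and PEG the direction is assumed and the size is probably small. The case for change rests mainly on the integrity of the randomised comparison and on how little the repair costs.

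**What to change.** In the intervention-arm withdrawal section, delete the words that extend the data-validity rule to the analyses. State that the rule may end a participant's sessions, as it can now, but does not withdraw the participant from follow-up: the 6- and 12-month surveys are still offered, and VDW data are still collected as consent allows.

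In section 6.a, state that these participants stay in the primary analysis in their randomised arm. If particular self-reports are doubted, set them aside only in a labelled sensitivity analysis. Use a written criterion applied identically to the 6- and 12-month surveys of both arms by someone who does not know the arm.

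The cost is a few sentences across the two sections, plus continued survey contact with a few people. The downside is that a few noisy self-reports remain in the primary PEG analysis.
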